5.4.2 Supportive Care Guidelines and Management Adverse Immune-Related Adverse Events (irAEs)

Subjects should receive appropriate supportive care measures as deemed necessary by the treating investigator. Suggested supportive care measures for the management of adverse events with potential immunologic etiology are outlined below. Where appropriate, these guidelines include the use of oral or intravenous treatment with corticosteroids as well as additional anti-inflammatory agents if symptoms do not improve with administration of corticosteroids. Note that several courses of steroid tapering may be necessary as symptoms may worsen when the steroid dose is decreased. For each disorder, attempts should be made to rule out other causes such as metastatic disease or bacterial or viral infection, which might require additional supportive care. The treatment guidelines are intended to be applied when the investigator determines the events to be related to pembrolizumab.

Note: if after the evaluation the event is determined not to be related, the investigator does not need to follow the treatment guidance (as outlined below). Refer to Section 6 for dose modification.

It may be necessary to perform conditional procedures such as bronchoscopy, endoscopy, or skin photography as part of evaluation of the event.

- **Pneumonitis:**

- For **Grade 2 events**, treat with systemic corticosteroids. When symptoms improve to Grade 1 or less, steroid taper should be started and continued over no less than 4 weeks.
- For **Grade 3-4 events**, immediately treat with intravenous steroids. Administer additional anti-inflammatory measures, as needed.

Add prophylactic antibiotics for opportunistic infections in the case of prolonged steroid administration.

- **Diarrhea/Colitis:**

Subjects should be carefully monitored for signs and symptoms of enterocolitis (such as diarrhea, abdominal pain, blood or mucus in stool, with or without fever) and of bowel perforation (such as peritoneal signs and ileus).

- All subjects who experience diarrhea/colitis should be advised to drink liberal quantities of clear fluids. If sufficient oral fluid intake is not feasible, fluid and electrolytes should be substituted via IV infusion. For Grade 2 or higher diarrhea, consider GI consultation and endoscopy to confirm or rule out colitis.
- For **Grade 2 diarrhea/colitis**, administer oral corticosteroids.
- For **Grade 3 or 4 diarrhea/colitis**, treat with intravenous steroids followed by high dose oral steroids.
- When symptoms improve to Grade 1 or less, steroid taper should be started and continued over no less than 4 weeks.

- **Type 1 diabetes mellitus (if new onset, including diabetic ketoacidosis [DKA]) or \geq Grade 3 Hyperglycemia, if associated with ketosis (ketonuria) or metabolic acidosis (DKA)**

- For **T1DM or Grade 3-4 Hyperglycemia**
 - Insulin replacement therapy is recommended for Type I diabetes mellitus and for Grade 3-4 hyperglycemia associated with metabolic acidosis or ketonuria.
 - Evaluate patients with serum glucose and a metabolic panel, urine ketones, glycosylated hemoglobin, and C-peptide.

- **Hypophysitis:**

- For **Grade 2 events**, treat with corticosteroids. When symptoms improve to Grade 1 or less, steroid taper should be started and continued over no less than 4 weeks.

Replacement of appropriate hormones may be required as the steroid dose is tapered.

- For **Grade 3-4** events, treat with an initial dose of IV corticosteroids followed by oral corticosteroids. When symptoms improve to Grade 1 or less, steroid taper should be started and continued over no less than 4 weeks. Replacement of appropriate hormones may be required as the steroid dose is tapered.

- **Hyperthyroidism or Hypothyroidism:**

Thyroid disorders can occur at any time during treatment. Monitor patients for changes in thyroid function (at the start of treatment, periodically during treatment, and as indicated based on clinical evaluation) and for clinical signs and symptoms of thyroid disorders.

- **Grade 2** hyperthyroidism events (and **Grade 2-4** hypothyroidism):
 - In hyperthyroidism, non-selective beta-blockers (e.g. propranolol) are suggested as initial therapy.
 - In hypothyroidism, thyroid hormone replacement therapy, with levothyroxine or liothyroinine, is indicated per standard of care.
- **Grade 3-4** hyperthyroidism
 - Treat with an initial dose of IV corticosteroid followed by oral corticosteroids. When symptoms improve to Grade 1 or less, steroid taper should be started and continued over no less than 4 weeks. Replacement of appropriate hormones may be required as the steroid dose is tapered.

- **Hepatic:**

- For **Grade 2** events, monitor liver function tests more frequently until returned to baseline values (consider weekly).
 - Treat with IV or oral corticosteroids
- For **Grade 3-4** events, treat with intravenous corticosteroids for 24 to 48 hours.
- When symptoms improve to Grade 1 or less, a steroid taper should be started and continued over no less than 4 weeks.

- **Renal Failure or Nephritis:**

- For **Grade 2** events, treat with corticosteroids.
- For **Grade 3-4** events, treat with systemic corticosteroids.
- When symptoms improve to Grade 1 or less, steroid taper should be started and continued over no less than 4 weeks.

- **Management of Infusion Reactions:** Signs and symptoms usually develop during or shortly after drug infusion and generally resolve completely within 24 hours of completion of infusion.

Table 1 below shows treatment guidelines for subjects who experience an infusion reaction associated with administration of pembrolizumab (MK-3475).

Table 1. Infusion Reaction Treatment Guidelines

NCI CTCAE Grade	Treatment	Premedication at subsequent dosing
Grade 1 Mild reaction; infusion interruption not indicated; intervention not indicated	Increase monitoring of vital signs as medically indicated until the subject is deemed medically stable in the opinion of the investigator.	None
Grade 2 Requires infusion interruption but responds promptly to symptomatic treatment (e.g., antihistamines, NSAIDS, narcotics, IV fluids); prophylactic medications indicated for <=24 hrs	
Stop Infusion and monitor symptoms. Additional appropriate medical therapy may include but is not limited to:
 
IV fluids Antihistamines NSAIDS Acetaminophen Narcotics
 
Increase monitoring of vital signs as medically indicated until the subject is deemed medically stable in the opinion of the investigator.
 
If symptoms resolve within one hour of stopping drug infusion, the infusion may be restarted at 50% of the original infusion rate (e.g., from 100 mL/hr to 50 mL/hr).
 
Otherwise dosing will be held until symptoms resolve and the subject should be premedicated for the next scheduled dose.
 
Subjects who develop Grade 2 toxicity despite adequate premedication should be permanently discontinued from further trial treatment administration.
	
Subject may be premedicated 1.5h (\pm 30 minutes) prior to infusion of pembrolizumab (MK-3475) with:
 
Diphenhydramine 50 mg po (or equivalent dose of antihistamine).
 
Acetaminophen 500-1000 mg po (or equivalent dose of antipyretic).

Grades 3 or 4	
Stop Infusion. Additional appropriate medical therapy may include but is not limited to:
 
IV fluids Antihistamines NSAIDS Acetaminophen Narcotics Oxygen Pressors Corticosteroids Epinephrine
 
Increase monitoring of vital signs as medically indicated until the subject is deemed medically stable in the opinion of the investigator.
 
Hospitalization may be indicated.
 
Subject is permanently discontinued from further trial treatment administration.
	No subsequent dosing
Appropriate resuscitation equipment should be available in the room and a physician readily available during the period of drug administration.		

Detailed guidelines for management of irAEs are provided in Table 3.

5.4.3 Contraception

Pembrolizumab may have adverse effects on a fetus *in utero*. Furthermore, it is not known if pembrolizumab has transient adverse effects on the composition of sperm.

For this trial, male subjects will be of non-reproductive potential if they have azoospermia (whether due to having had a vasectomy or due to an underlying medical condition).

Female subjects will be considered of non-reproductive potential if they are either:

- (1) Postmenopausal (defined as at least 12 months with no menses without an alternative medical cause; in women < 45 years of age a high follicle stimulating hormone (FSH) level in the postmenopausal range may be used to confirm a post-menopausal state in women not using hormonal contraception or hormonal replacement therapy. In the absence of 12 months of amenorrhea, a single FSH measurement is insufficient.);

OR

- (2) Have had a hysterectomy and/or bilateral oophorectomy, bilateral salpingectomy or bilateral tubal ligation/occlusion, at least 6 weeks prior to screening;

OR

- (3) Has a congenital or acquired condition that prevents childbearing.

Female and male subjects of reproductive potential must agree to avoid becoming pregnant or impregnating a partner, respectively, while receiving study drug and for 120 days after the last dose of study drug by complying with one of the following:

- (1) Practice abstinence[†] from heterosexual activity;

OR

- (2) Use (or have their partner use) acceptable contraception during heterosexual activity.

Acceptable methods of contraception are[‡]:

- (1) Single method (one of the following is acceptable):

- (a) Intrauterine device (IUD)
 - (i) Vasectomy of a female subject's male partner
 - (ii) Contraceptive rod implanted into the skin

- (2) Combination method (requires use of two of the following):

- (a) diaphragm with spermicide (cannot be used in conjunction with cervical cap/spermicide)
- (b) cervical cap with spermicide (nulliparous women only)
- (c) contraceptive sponge (nulliparous women only)

- (d) male condom or female condom (cannot be used together)
- (e) hormonal contraceptive: oral contraceptive pill (estrogen/progestin pill or progestin-only pill), contraceptive skin patch, vaginal contraceptive ring, or subcutaneous contraceptive injection

†Abstinence (relative to heterosexual activity) can be used as the sole method of contraception if it is consistently employed as the subject's preferred and usual lifestyle and if considered acceptable by local regulatory agencies and ERCS/IRBs. Periodic abstinence (e.g., calendar, ovulation, sympto-thermal, post-ovulation methods, etc.) and withdrawal are not acceptable methods of contraception.

‡If a contraceptive method listed above is restricted by local regulations/guidelines, then it does not qualify as an acceptable method of contraception for subjects participating at sites in this country/region.

Subjects should be informed that taking the study medication may involve unknown risks to the fetus (unborn baby) if pregnancy were to occur during the study. To participate in the study subjects of childbearing potential must adhere to the contraception requirement (described above) from the day of study medication initiation (or 14 days prior to the initiation of study medication for oral contraception) throughout the study period up to 120 days after the last dose of trial therapy. If there is any question that a subject of childbearing potential will not reliably comply with the requirements for contraception, that subject should not be enrolled on the study.

5.4.4 Use in Pregnancy

If a subject inadvertently becomes pregnant while on treatment with pembrolizumab, the subject will immediately be removed from the study. The site will contact the subject at least monthly and document the subject's status until the pregnancy has been completed or terminated. The outcome of the pregnancy will be reported to the principal investigator and to Merck without delay and within 24 hours to the principal investigator and within 2 working days to Merck if the outcome is a serious adverse experience (e.g., death, abortion, congenital anomaly, or other disabling or life-threatening complication to the mother or newborn).

The study investigator will make every effort to obtain permission to follow the outcome of the pregnancy and report the condition of the fetus or newborn to Merck. If a male subject impregnates his female partner the study personnel at the site must be informed immediately and the pregnancy reported to the principal investigator and to Merck and followed as described above and in Section 7.3.4.

5.4.5 Use in Nursing Women

It is unknown whether pembrolizumab is excreted in human milk. Since many drugs are excreted in human milk, and because of the potential for serious adverse reactions in the nursing infant, subjects who are breast-feeding are not eligible for enrollment.

5.5 Criteria for Taking a Participant off Protocol Therapy

Duration of therapy will depend on individual response, evidence of disease progression and tolerance. In the absence of treatment delays due to adverse event(s), treatment may continue for

35 cycles until one of the following criteria applies:

- Disease progression
- Intercurrent illness that prevents further administration of treatment
- Unacceptable adverse event(s)
- Participant demonstrates an inability or unwillingness to comply with the oral medication regimen and/or documentation requirements
- Participant decides to withdraw from the protocol therapy
- General or specific changes in the participant's condition render the participant unacceptable for further treatment in the judgment of the treating investigator

Participants will be removed from the protocol therapy when any of these criteria apply. The reason for removal from protocol therapy, and the date the participant was removed, must be documented in the case report form (CRF). Alternative care options will be discussed with the participant.

In the event of unusual or life-threatening complications, treating investigators must immediately notify the Overall PI, [name] at [contact] ([name]).

5.6 Duration of Follow Up

Participants will be followed for survival every 12 weeks (\pm 14 days) for 24 months after completion of protocol therapy, discontinuation of protocol therapy or until death, whichever occurs first. Survival follow-up may be conducted by telephone or email contact with the participant or his/her primary physician. Participants removed from protocol therapy for unacceptable adverse event(s) will be followed until resolution or stabilization of the adverse event regardless of the duration of follow-up required.

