5. TREATMENT PLAN

5.1 Treatment Regimen

The rationale for selection of doses to be used in this trial is provided in Section 2.3 – Rationale.

Details on preparation and administration of pembrolizumab are provided in the Pharmacy Manual.

Pembrolizumab will be administered once every 3 weeks, with 21 consecutive days defined as a treatment cycle (unless the treatment cycle length is increased for adverse effect, as detailed in Section 6). Treatment will be administered on an outpatient basis. Reported adverse events and

potential risks are described in Section 7. No dose reductions are allowed. No investigational or commercial agents or therapies other than those described below may be administered with the intent to treat the participant's malignancy.

All participants will receive pembrolizumab at a fixed dose of 200 mg intravenously every 3 weeks for up to 35 cycles (approximately 2 years) or until disease progression, prohibitive toxicity, withdrawal of consent, or investigator discretion.

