11. MEASUREMENT OF EFFECT

11.1 Response Criteria

The primary objective of this study is overall response rate (ORR). Response and progression will be evaluated following the 2014 Lugano criteria for the primary endpoint and LyRIC for secondary endpoint. Patients will undergo tumor restaging, using the appropriate combination of imaging and bone marrow biopsies, after cycles 2 and 5 and 8 and then every 4 cycles thereafter until cycle 32. Radiographic restaging will also be performed at the 60-day post-treatment follow-up visit and at pre-specified intervals thereafter (see Study Calendar, section 10). Imaging will consist of PET/CT scans until the patient has achieved a metabolic CR (defined as Deauville score 1-3) at which juncture transition to CT of the chest, abdomen and pelvis will be acceptable at the discretion of the treating physician. Response assessment will follow standard criteria (Lugano criteria) for lymphoma. Bone marrow biopsy will be required within 30 days of radiology testing to confirm CR for patients with marrow involvement at baseline. A repeat bone marrow biopsy is not necessary to confirm CR if there was no marrow involvement at baseline.

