11.2.2 Progression-Free Survival

Overall Survival: Overall Survival (OS) is defined as the time from randomization (or registration) to death due to any cause, or censored at date last known alive.

Progression-Free Survival: Progression-Free Survival (PFS) is defined as the time from randomization (or registration) to the earlier of progression or death due to any cause. Participants alive without disease progression are censored at date of last disease evaluation.

For patients with progression of disease on imaging, it is strongly recommended that a confirmatory biopsy be obtained whenever possible.

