13.2.2 Statistical considerations

The hypothesis of this trial is that the response rate of pembrolizumab in this patient population will be 40% or higher. Assuming at least 20 patients are enrolled, we would consider the treatment promising if at least 6 patients respond. With this design, the study would have approximately 87% power to detect a difference in the response rate between 15% (the null hypothesis) and 40% (the alternative hypothesis), at a significance level of 0.07 (based on the exact binomial distribution). The maximal 90% confidence interval around the estimates for response and toxicity will be approximately +/-20%.

We anticipate accrual of 1 patient per month yielding an accrual period of 24 months. We anticipate following the last patient accrued for 6 months before being able to determine best overall response (the primary endpoint). Patients will be followed for 2 years after accrual for secondary endpoints such as PFS, OS, and duration of response for total study duration of approximately 4 years.

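### Sections 5.6, 13.2.2 and study calendar footnote e give conflicting overall survival follow-up rules; under 5.6 censoring depends on time on therapy, so the Kaplan-Meier tail beyond about 26 months may be biased, probably upward (minor).

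*Combined protocol and SAP*

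**What the plan says.** Three places govern how long survival is followed.

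- Section 5.6 starts the clock when therapy ends: survival contact every 12 weeks "for 24 months after completion of protocol therapy, discontinuation of protocol therapy or until death, whichever occurs first".
- Section 13.2.2 starts it at accrual: "Patients will be followed for 2 years after accrual for secondary endpoints such as PFS, OS, and duration of response". It puts the whole study at about 4 years. It does not say whether accrual means each participant's own registration or the close of accrual.
- Study calendar footnote e moves participants to 12-weekly telephone or e-mail contact after progression or new treatment and names no end.

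Section 11.2.2 censors OS at the date last known alive: "Overall Survival (OS) is defined as the time from randomization (or registration) to death due to any cause, or censored at date last known alive". Section 13.6 estimates time-to-event endpoints by Kaplan-Meier and follow-up time by reverse Kaplan-Meier. It gives no data cut-off, truncation point or sensitivity analysis for censoring. Under section 5.5, duration of therapy depends on response, progression and tolerance.

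**The concern.** The date last known alive cannot fall after contact ends, so the follow-up rule sets the censoring date. Under 5.6 that date is a function of time on therapy, which is itself an outcome. A participant who stops at the first restaging leaves OS follow-up about two years before one who completes treatment. From that point the risk set shifts towards people who stayed on therapy longer. Kaplan-Meier needs the people censored at a given time to have the same later hazard as those who remain. Here that is doubtful.

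At stake is the OS curve beyond about two years, and the reverse Kaplan-Meier follow-up time, which would mix short follow-up of early failures with long follow-up of responders. The end of the study is also left uncertain. Section 14 ties it to the section on sample size, accrual and duration, and the publication deadlines run from it.

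**Working it through.** **1. The plan's own duration.** Accrual: "We anticipate accrual of 1 patient per month yielding an accrual period of 24 months". Then 24 months of accrual + 24 months of follow-up = 48 months, which reproduces the stated 4 years. Both readings of 2 years after accrual give this total, because the last participant reaches 24 months at month 48 either way.

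**2. Duration under 5.6.** Longest therapy (section 5.1): 35 cycles × 3 weeks = 105 weeks = 24.1 months, with the last dose at week 102 = 23.5 months. For a participant enrolled at month 24, follow-up ends at 24 + 23.5 + 24 = 71.5 to 24 + 24.1 + 24 = 72.1 months. Neither reading of 13.2.2 gives this.

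**3. When OS follow-up ends under 5.6.** Limit = time on therapy + 24 months. The first restaging is after cycle 2, week 6 (section 11.1: "after cycles 2 and 5 and 8 and then every 4 cycles thereafter until cycle 32").

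| Therapy stops | Months on therapy | OS follow-up ends (months from start) |
|---|---|---|
| Week 6 | 1.4 | 25.4 |
| Week 9 | 2.1 | 26.1 |
| Week 15 | 3.4 | 27.4 |
| Weeks 102-105 | 23.5-24.1 | 47.5-48.1 |

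With a cut-off 24 months after the last registration, potential follow-up is 24 to 48 months and depends on entry date alone.

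**4. Size of the possible bias.** The documents give no survival figures for participants on or after pembrolizumab, so every survival input from here on is an assumption.

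Let a fraction f stop early with median OS mE and the rest have median mL, both exponential. True survival is S(t) = f·2^(−t/mE) + (1−f)·2^(−t/mL). If early stoppers still alive are censored at time c, the large-sample Kaplan-Meier value for t > c is S(c)·2^(−(t−c)/mL).

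Example with f = 0.6, mE = 12, mL = 48, c = 26:

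- True 36-month OS: 0.6 × 0.125 + 0.4 × 0.595 = 31.3%.
- S(26) = 0.6 × 0.223 + 0.4 × 0.687 = 40.8%.
- Kaplan-Meier at 36 months: 40.8% × 0.866 = 35.3%, about 4 points too high.

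A simulation of this setting (24 patients, one per month, 2,000 replicates) gives 35.5% under 5.6 and 31.6% with a common cut-off. The standard error is about 10 points.

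Other settings, Kaplan-Meier minus truth at 36 months:

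| Assumptions | Difference (points) |
|---|---|
| Simulation: responder median 48; non-responder median 8, 12, 18; 40% response | +3, +4, +4 |
| Same, 15% response | +4, +5, +6 |
| Simulation: 60% early progressors; median survival after progression 6, 12, 24 months | about +2, +4, +4 |
| Formula, c = 25.4: f = 0.4 or 0.6; mE = 6, 12, 24; mL = 24, 36, 60; unequal hazards | +0.9 to +4.8 |
| Formula, equal hazards (mE = mL = 24) | 0 |
| Formula, f = 0.6; 20% of early stoppers are long-term survivors, the others have median 6; mL = 36 or 24 | −0.9 or −2.0 |

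The smallest positive values arise when early stoppers have a median of 6 months, because few are then alive to be censored. At 48 months the formula gives 0 to +7.2 points, and −2.8 to −4.6 in the reversed case.

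**5. Precision.** With 30 patients, the second simulation leaves about 5 to 7 at risk at 36 months under 5.6, and about 3 to 4 if a 48-month data cut is also applied.

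**The case against.** A reader might infer that OS beyond about 26 months is overstated. The documents do not support that as a fact. It requires early stoppers who are alive two years after stopping to have a higher later hazard than everyone else, and no section gives such a figure. With equal hazards the bias vanishes; with long-term survivors among early progressors it reverses. Section 1.1 also lists sustained complete response as a reason to stop, so some good responders could leave follow-up early. Section 2.1 says that most patients with relapsed or refractory peripheral T-cell lymphoma die within a year; if that held more widely, few early progressors would remain to be censored. All of this stands. It limits the direction and size of the bias, but leaves censoring tied to outcome.

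A second objection is that 5.6 may not govern. Footnote e covers exactly the early progressors and has no end date, and 13.2.2 read per participant stops at 24 months, where the problem does not arise. This stands in part: the conflict is three-way, and the bias arises only if 5.6 is followed. But footnote e sets a contact frequency, while 5.6 names an explicit end, so a site could reasonably stop contact as 5.6 says.

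Third, the stakes are small. OS is not among the objectives in section 1.3 and appears only as a reported endpoint in 13.1 and 13.6. No 36-month estimate or external OS comparison is planned. At 40% response (24 patients; non-responder medians 8, 12, 18 months), the root mean squared error of 36-month OS is 0.100, 0.110 and 0.117 under 5.6, against 0.096, 0.102 and 0.105 with a common cut-off. The gap can be wider at 15% response (for example 0.117 against 0.090). This stands, and it is why the point is minor.

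**Conclusion.** The contradiction is certain: about 72 months under 5.6 against 48 under 13.2.2, with an open end in footnote e. It is also certain that 5.6 makes the OS censoring time depend on time on therapy, with the earliest progressors leaving at about 25-26 months.

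That the OS tail is then biased is possible, and upward is the likelier direction. The simulations put it at about +2 to +6 points at 36 months, or 0.3 to 0.7 standard errors in the first of them. This rests on assumed exponential survival with a worse prognosis in early stoppers. A firm statement that OS is overstated goes beyond the documents. OS to 24 months is unaffected, provided contact is actually made up to the 24-month limit, and the primary response-rate test is untouched. Severity: minor.

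**What to change.** Reconcile 5.6, 13.2.2 and footnote e into one OS follow-up rule, and state whether 2 years after accrual runs from each participant's registration or from the close of accrual. Then take one of two routes.

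- **Common cut-off.** Follow every participant for survival to one date that does not depend on when therapy stopped, for example 24 months after the last registration, and censor OS administratively there. This keeps the 4-year total. It costs some extra telephone or e-mail contacts for early discontinuers, which 5.6 already allows. It also shortens OS follow-up for late registrants with long therapy: with 24 patients, 40% response and medians of 8 and 48 months, the number at risk at 36 months falls from 5.8 to 3.5.
- **Keep 5.6.** State in 13.6 that OS is estimated only to 24 months from registration. This gives up the tail. It also needs a closing contact: counted 12-weekly from the end of therapy, the last scheduled contact inside 24 months is at week 96 (22.1 months), so a week-6 stopper could be last known alive at about 1.4 + 22.1 = 23.5 months.
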